- Sample size: TARN/EMS data suggests approximately 200 major trauma cases (ISS>15) per 4 months per trauma network. Assuming a target sensitivity of 95% as per American College of Surgeons Committee on Trauma (ASCOT) guidance, the total of 800 reference standard positive cases would give a 95% confidence interval coverage of 2% for sensitivity. EMS data suggests approximately 25,000 patients presenting with injury over 4 months per trauma network (total 100,000 across all 4 of the participating trauma networks). Assuming a target specificity of 70% as per ASCOT guidance, coding 2000 reference standard negative cases (sampling fraction of 2%) would give a 95%CI coverage of 2% for specificity. The total sample size of 2,800 cases would equate to an approximate total of 700 patients (200 major trauma cases and 500 non-major trauma cases) per network. This should be a manageable work load for research paramedics (approximately 9 cases to code per working day), while providing sufficient statistical power.

The following table presents the precision achieved for a range of observed sensitivities and specificities with the proposed sample size:

Estimated	Precisio	Level of	LCL	UCL	Reference standard
sensitivity	n	confidence			positive N=
0.97	0.0125	0.95	0.95 8	0.98 3	716
0.95	0.015	0.95	0.93 5	0.96 5	811
0.90	0.02	0.95	0.88 0	0.92 0	865
0.80	0.03	0.95	0.77 0	0.83 0	683
0.70	0.03	0.95	0.67 0	0.73 0	897
0.60	0.035	0.95	0.56 5	0.63 5	753
0.50	0.035	0.95	0.46 5	0.53 5	784
Estimated	Precisio	Level of	LCL	UCL	Reference standard
Specificity	n	confidence			negative
					N=
			0.96	0.97	
0.97	0.0075	0.95	3	8	1988
			0.94	0.96	
0.95	0.01	0.95	0	0	1825
			0.88	0.91	
0.9	0.0125	0.95	8	3	2213
			0.78	0.81	
0.8	0.0175	0.95	3	8	2007
			0.68	0.72	
0.7	0.02	0.95	0	0	2017
			0.57	0.62	
0.6	0.0225	0.95	8	3	1822
			0.47	0.52	
0.5	0.0225	0.95	8	3	1898

• **Outputs:** Optimally performing candidate triage tool identified by expert consensus, PPI and participating trauma networks.

c) Phase Three - Evaluation of System-Level Performance of Implemented Optimal Triage Tool.

A service evaluation characterising under/over-triage rates of the candidate triage tool when implemented operationally:

- Setting: Major trauma network within each of the West Midlands, Yorkshire, South Western and London Ambulance Services.
- Study population: Any patient attended by EMS following injury. Sub-group analyses of children (<16 years) and elderly patients (≥65 years).
- Study sample:

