Patient identifiable data (names, date of birth, and contact details) will not be collected or stored. The study manager, data managers, CI, research paramedics and administrators will have access to anonymised data on the study database, through the use of usernames and encrypted passwords. The Sponsor will permit monitoring and audits by the relevant authorities, including the Research Ethics Committee. The CI will also allow monitoring and audits by these bodies and the Sponsor, providing direct access to source data and all study documentation. All data will be collected and retained in accordance with the Data Protection Act 1998, European Union General Data Protection Regulations (GDPR) 2018, HRA Confidentiality Approval Group (CAG) approvals, and University of Sheffield CTRU SOPs. Output for analysis will be generated in a format and at intervals to be agreed between Sheffield CTRU and the CI.

Sample size calculation

TARN/EMS data suggests approximately 200 major trauma cases (ISS>15) per 4 months per trauma network. Assuming a target sensitivity of 95% as per American College of Surgeons Committee on Trauma (ASCOT) guidance, the total of 800 reference standard positive cases would give a 95% confidence interval coverage of 2% for sensitivity. EMS data suggests approximately 25,000 patients presenting with injury over 4 months per trauma network (total 100,000 across all 4 of the participating trauma networks). Assuming a target specificity of 70% as per ASCOT guidance, coding 2000 reference standard negative cases (sampling fraction of 2%) would give a 95%CI coverage of 2% for specificity. The total sample size of 2,800 cases would equate to an approximate total of 700 patients (200 major trauma cases and 500 non-major trauma cases) per network. This should be a manageable work load for research paramedics (approximately 9 cases to code per working day), while providing sufficient statistical power.

Statistical analyses

Full details of planned analyses will be contained in a specific statistical analysis plan (SAP), which will conform to Sheffield CTRU SOP ST001. Sample derivation and data linkages will be presented with a STROBE flow diagram.

The Phase Two validation study will be conducted, reported and presented according to the latest STARD 2015 guidelines for diagnostic accuracy studies.[37, 38] Under-triage is defined as the proportion of patients who could benefit from specialist care not transported to a

MATTS Study

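### Phase Two sample size: the text gives 2% precision for sensitivity with 800 cases, but its inputs and the protocol's own table give about 1.5%, and the table is mislabelled

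*Protocol*

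**What the plan says.** The Phase Two sample size paragraph appears twice in the Protocol, in the Scientific Summary (Phase Two, Sample size) and in section 5.1 (Sample size calculation).

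- Sensitivity: "Assuming a target sensitivity of 95% as per American College of Surgeons Committee on Trauma (ASCOT) guidance", it states that "the total of 800 reference standard positive cases would give a 95% confidence interval coverage of 2% for sensitivity".
- Specificity: on an assumed value of 70%, taken from the same source, it states that "coding 2000 reference standard negative cases (sampling fraction of 2%) would give a 95%CI coverage of 2% for specificity".

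Only the Scientific Summary adds a table, which it says "presents the precision achieved for a range of observed sensitivities and specificities with the proposed sample size". For sensitivity 0.95 the table gives precision 0.015, limits 0.935 and 0.965, and N = 811. The N column varies by row: 683 to 897 for reference standard positives and 1,822 to 2,213 for reference standard negatives.

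**The concern.** The headline precision for sensitivity does not follow from its stated inputs and disagrees with the table that accompanies it in the Scientific Summary. Section 5.1 repeats the 2% without the table, so a reader of the main section sees only that figure. The table's description also does not match its contents: it claims to show what the proposed sample achieves, but its N is never the proposed 800 or 2,000.

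Sensitivity (1 − under-triage) is a main outcome and the design is described by precision, so this figure should be right and should be the same throughout. The two values imply different numbers of positives (about 457 for ±2%, 811 for ±1.5%). If accrual or linkage falls short of 800, anyone judging whether the sample still suffices has two benchmarks.

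**Working it through.** **Inputs.** Sensitivity 0.95 with 800 positives and specificity 0.70 with 2,000 negatives (section 5.1, Sample size calculation; same in the Scientific Summary); 95% two-sided confidence, z = 1.96; table rows from the Scientific Summary.

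**Formulas.** Half-width d = z√(p(1 − p)/n); required number n = z²p(1 − p)/d².

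**Step 1: what the stated percentage means.** Specificity: 1.96 × √(0.70 × 0.30/2,000) = 0.0201. The stated 2% is reproduced as a half-width; the full width would be 4.02 points. In this paragraph the figure is therefore a half-width.

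**Step 2: the sensitivity figure.** 1.96 × √(0.95 × 0.05/800) = 0.0151, or 1.51 points. The stated 2% is not reproduced. Alternatives at p = 0.95, n = 800:

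- full width: 3.02 points
- continuity-corrected half-width: 1.57 points
- Wilson interval: 93.3% to 96.3%
- Clopper-Pearson interval: 93.3% to 96.4%, longer arm 1.75 points
- one-sided 95%: 1.27 points
- 99% half-width: 1.98 points, but the text states 95%

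Inverting the formula, ±2% needs 1.96² × 0.0475/0.02² = 456.2, so 457 cases. ±1.5% needs 1.96² × 0.0475/0.015² = 811.0, which is the table's N.

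**Step 3: the table.** All 14 rows reproduce, to within one case, as n = z²p(1 − p)/d². They were solved for N at a chosen d. Evaluated at the proposed numbers instead (percentage points):

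| Sensitivity | Table d (N) | d at 800 | Difference |
|---|---|---|---|
| 0.97 | 1.25 (716) | 1.18 | −0.07 |
| 0.95 | 1.50 (811) | 1.51 | +0.01 |
| 0.90 | 2.00 (865) | 2.08 | +0.08 |
| 0.80 | 3.00 (683) | 2.77 | −0.23 |
| 0.70 | 3.00 (897) | 3.18 | +0.18 |
| 0.60 | 3.50 (753) | 3.39 | −0.11 |
| 0.50 | 3.50 (784) | 3.46 | −0.04 |

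| Specificity | Table d (N) | d at 2,000 | Difference |
|---|---|---|---|
| 0.97 | 0.75 (1,988) | 0.75 | 0.00 |
| 0.95 | 1.00 (1,825) | 0.96 | −0.04 |
| 0.90 | 1.25 (2,213) | 1.31 | +0.06 |
| 0.80 | 1.75 (2,007) | 1.75 | 0.00 |
| 0.70 | 2.00 (2,017) | 2.01 | +0.01 |
| 0.60 | 2.25 (1,822) | 2.15 | −0.10 |
| 0.50 | 2.25 (1,898) | 2.19 | −0.06 |

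Six rows list an N above plan (811, 865, 897; 2,213, 2,007, 2,017). In three of these (811, 2,007, 2,017) the difference is about 0.01 points or less. The other eight rows need fewer cases than planned.

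**The case against.** **Rounding.** 1.51 rounds to 2 in whole percents, both Phase Two figures are whole percents, and the exact interval's longer arm is 1.75 points. This makes loose rounding a plausible origin, but it does not remove the disagreement with the table's 0.015. Nor does the protocol round to whole percents throughout. Phase Three quotes ±1.0% and ±1.5%, where the same formula gives 1.23 (0.95, 1,200 cases) and 1.64 (0.70, 3,000 cases). Whole-percent rounding would turn 1.64 into 2. Rounding to half points fits both Phase Three figures, and would turn 1.51 into 1.5.

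**No harm from the text error.** This stands. The stated width is larger than the actual one, so nobody relying on it is let down.

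**The table discloses its N.** This also stands. Each row prints its own N, so a careful reader can see how it was built. A reader might infer that the table promises precision the study will not deliver. That is too strong: most rows are met or bettered at 800 and 2,000, and the visible shortfalls are 0.18 points at most, against a planned 800 that is itself built on an approximate yield per network.

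**The sample size does not rest on these figures alone.** This stands too. The positives are described as a census sample, and 800 is 4 networks × about 200 expected cases. The paragraph also defends the total of 2,800 by coding workload. A reader might infer from the 457 that the study is oversized, or from the table that it is undersized. The documents support neither.

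**Conclusion.** The point holds as a minor correction of a stated precision figure. With 800 positives at 95% sensitivity the 95% half-width is about 1.5 points (1.51), not 2, as the protocol's own table shows. The stated half-width is about a third too large (2.0/1.51 = 1.32), in the conservative direction. The table lists required numbers under a description that says achieved precision. At the proposed 800 and 2,000 its half-widths are off by at most about 0.23 points. They are visibly worse only at sensitivity 0.90 (2.08 against 2.00), sensitivity 0.70 (3.18 against 3.00) and specificity 0.90 (1.31 against 1.25).

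This assumes simple binomial sampling with the normal approximation, which is what the table itself uses, and that 800 and 2,000 cases are actually analysed. The protocol states no precision threshold for choosing the candidate tool, so no decision rule is affected.

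**What to change.** - In the Scientific Summary (Phase Two, Sample size) and in section 5.1 (Sample size calculation), replace 2% with ±1.5% for sensitivity, and call the quantity a half-width in both sentences. The ±2% for specificity at 2,000 cases can stay.
- For the table in the Scientific Summary, either recompute every row at fixed N = 800 and N = 2,000, using the values shown above, or keep the numbers and retitle it as the number of cases required for each stated precision.

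The cost is two wording changes and one recomputed or retitled table. If the table is recomputed, a few rows become slightly wider and others slightly narrower. Enrolment, data collection and analysis are unchanged.

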 - **Setting:** 4 major trauma networks within the West Midlands, Yorkshire, South Western and London Ambulance Services.
 - **Study design:** Single gate diagnostic accuracy cohort study with a census sample of reference standard positive major trauma cases; and random sample of reference standard negative cases without major trauma.
 - **Study population:** Patients attended by ambulance following injury. Sub-group analyses of children (<16 years) and elderly patients (≥65 years).
 - Study sample:
 - Reference standard positive cases: Census sample of consecutive cases meeting MATTS reference standard /secondary reference standards, identified through augmented TARN processes.
 - *Reference standard negative cases:* Random sample of cases presenting to EMS with injury. Appropriate patients identified using injury related working impression codes, use of major trauma interventions, hospital trauma team pre-alerts, and call priority.

Data collection:

- Ambulance service data: fixed fields used as recorded in EPR. Free text fields coded by research paramedics blinded to reference standard.
- TARN data: Fixed fields as recorded in TARN database. Additional MATTS required data fields completed by TARN data coordinators/research paramedics as required.
- Data linkage: Research paramedics to review all reference standard positive cases and manually determine a definitive EMS identifier for deterministic linkage. Non-linked cases assumed to be reference standard negative.
- Data governance: The proposed study design change does not affect data flows; and CAG and ethics approvals should be unaffected.
- Index tests: Existing and expert consensus-derived major trauma triage tools scored according to observed pre-hospital variables by blinded research paramedics. Identifiable data and reference standard classification withheld from research paramedics during triage tool coding.
- Reference standard: Patients with the potential to benefit from MTC care previously defined by independent expert consensus (clinicians, stakeholders) and Patient and Public Involvement (PPI) consultation. Secondary reference standards of Injury Severity Score (ISS) >15 and US consensus definition. Major trauma cases identified through augmented TARN case ascertainment process, supported by MATTS research paramedics.
- **Outcomes:** Sensitivity/specificity (corresponding to 1-Under/over-triage rates).

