In Phase Two, routinely collected anonymised data will be used to score triage tools and patient care will be unaffected. We will therefore not seek individual participant consent, but will confirm approval from the HRA Confidentiality Advisory Group (CAG) and a NHS REC to link and analyse de-identified anonymised linked data.

Data collection - Index test / triage tool variables and decisions

Anonymised demographic, clinical and injury information will be collated from EMS electronic PRFs. Results of currently used triage tools (i.e. whether the currently used triage tool 'triggered') and hospital destination will also be collected. LAS paper PRFs are scanned with computerised extraction of basic demographic and clinical data; additional patient data, not extracted by scanning, will be abstracted manually by research paramedics. Collated EMS data will then be coded to score whether triage tools are positive or negative and allow calculation of under-/overtriage against the reference standard described below.

Data collection - reference standard / major trauma classification

The presence of major trauma in patients conveyed to hospital by EMS following injury will be determined by a comprehensive case finding process performed in conjunction with the English national trauma registry, TARN.

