MTC, this corresponds to 1 – sensitivity. Over-triage is defined as the proportion of patients incorrectly transported to the MTC, this corresponds to 1 – specificity. We will summarise the baseline demographic and clinical characteristics of participants with appropriate summary statistics. The primary analysis will examine the protocol-based diagnostic accuracy of triage tools based on recorded EMS data, regardless of actual hospital destination using the primary reference standard. Under/over-triage, sensitivity, specificity, predictive values, and c-statistics with their 95% confidence intervals (95% CI), will be calculated for all included index tests. Differences in test performance will be tested using De Long's method for comparing c-statistics.

A secondary analysis will similarly evaluate the actual performance of triage tools currently used in participating trauma networks according to transport destination. Sensitivity analyses will be performed to explore the influence of missing data (including multiple imputation and scenario analyses where appropriate) and different gold standards (secondary reference standards e.g. ISS>15). Pre-specified sub-group analyses will include children (<16 years) and elderly patients (≥65 years); urban versus rural environments; and blunt versus penetrating trauma. Results of the Phase Two validation study will be presented to the expert advisory, participating trauma networks and PPI groups, and an optimally performing candidate triage tool chosen for refinement, implementation, and further investigation in the Phase Thee service evaluation study.

Safety reporting

In the MATTS Phase Two validation study, routinely collected anonymised data will be used to remotely score non-operational triage tools and patient care will be unaffected. Safety reporting is therefore not relevant.

6. Phase Three

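### The one between-tool test the protocol names, De Long's test of c-statistics, compares positive/negative triage tools only on the average of sensitivity and specificity, so it has little or no power against offsetting differences.

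*Protocol*

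**What the plan says.** Section 5.1 of the protocol (Data collection, index test) describes how the tools are scored: "Collated EMS data will then be coded to score whether triage tools are positive or negative". The Scientific Summary gives the Phase Two outcomes as "Sensitivity/specificity (corresponding to 1-Under/over-triage rates", that is, two separate quantities.

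The sample size paragraph in section 5.1 treats them separately too. For sensitivity it works from a 95% target: "the total of 800 reference standard positive cases would give a 95% confidence interval coverage of 2% for sensitivity". For specificity it uses a 70% target and 2,000 reference standard negative cases.

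Under Statistical analyses in section 5.1, each tool is to be estimated on its own: "Under/over-triage, sensitivity, specificity, predictive values, and c-statistics with their 95% confidence intervals (95% CI), will be calculated for all included index tests". The next sentence fixes the comparison between tools: "Differences in test performance will be tested using De Long's method for comparing c-statistics". The protocol names no paired comparison of sensitivity or of specificity. The results then go to the expert advisory group, the networks and the PPI groups, and one tool is chosen for Phase Three.

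**The concern.** A c-statistic is a natural summary for a score with many cut-points. For a tool that only says yes or no it is the plain average of sensitivity and specificity. A test of c-statistics then asks whether two tools have the same average, with one point of sensitivity worth exactly one point of specificity.

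That sits badly with a project built around the trade-off between under-triage and over-triage. Two tools that make this trade differently can have equal or nearly equal averages, and the named test then has little or nothing to detect. When the test is significant, it does not say whether the tools differ in under-triage, over-triage or both. At stake is the formal evidence on tool differences that accompanies the results used to pick a tool for operational use.

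**Working it through.** **Inputs.** From the protocol: 800 positives, 2,000 negatives, target sensitivity 95%, target specificity 70%, and about 100,000 injured patients over the Phase Two period. Assumed: a two-sided 5% level (taken from the 95% CIs) and the agreement between tools within each reference class, which the protocol does not give. Two extremes were run: conditionally independent tools and fully nested tools.

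**The protocol's own figures.** Half-width = 1.96 × √(p(1−p)/n).
- Sensitivity: 1.96 × √(0.95 × 0.05/800) = 1.51 points, which rounds to the stated 2%.
- Specificity: 1.96 × √(0.70 × 0.30/2000) = 2.01 points, as stated.

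All 14 sample sizes in the precision table of the Scientific Summary also reproduce. The sample size is not in dispute.

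**The c-statistic of a binary tool.** Take one positive and one negative case and count ties as ½:
c = Se × Sp + ½[Se(1−Sp) + (1−Se)Sp] = (Se + Sp)/2.
A numerical check of the De Long calculation gave the same value.

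**Standard error of the difference in c.** SE = ½√(V₁/800 + V₂/2000), where V₁ and V₂ are the variances of the within-patient difference between tools in positives and in negatives.

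For 95%/70% against 80%/85%, both c = (0.95 + 0.70)/2 = (0.80 + 0.85)/2 = 0.825, so the true difference is 0.
- Independent: V₁ = 0.0475 + 0.16 = 0.2075; V₂ = 0.21 + 0.1275 = 0.3375; SE = 0.0103.
- Nested: V₁ = V₂ = 0.15 − 0.15² = 0.1275; SE = 0.0075.

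The mean SEs in the simulation agree with these.

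**Simulated rejection rates** (4,000 studies per scenario; independent, then nested):

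| Tools (Se/Sp) | c-statistics | De Long | Paired test, Se | Paired test, Sp |
|---|---|---|---|---|
| 95/70 v 80/85 | 0.825, 0.825 | 5.1%, 4.2% | 100% | 100% |
| 95/70 v 85/80 | 0.825, 0.825 | 4.6%, 4.8% | 100% | 100% |
| 95/70 v 78/85 | 0.825, 0.815 | 16%, 24% | 100% | 100% |
| 95/70 v 80/80 | 0.825, 0.800 | 66%, 94% | 100% | 100% |

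The third row shows that exact equality is not needed: a 17-point gap in sensitivity is usually missed when the averages differ by one point. The fourth row shows that power returns as the averages separate.

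The protocol's Introduction quotes 66%/88% for the ASCOT tool (c = 0.77). A tool at 84%/70% has the same c, and De Long rejects in about 5% of runs despite an 18-point gap in each component.

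**In patients.** For 95%/70% against 80%/85%, missed cases among 800 positives are 800 × 0.05 = 40 against 800 × 0.20 = 160. Over-triaged patients among 100,000 − 800 = 99,200 negatives are 0.30 × 99,200 = 29,760 against 0.15 × 99,200 = 14,880. The named test treats these two tools as equal.

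**The case against.** The strongest reply is that the trade-off will be seen anyway. The sentence before the De Long sentence commits to sensitivity and specificity with 95% CIs for every tool. At the planned size, sensitivities of 95% and 80% would carry about ±1.5 and ±2.8 points, and specificities of 70% and 85% about ±2.0 and ±1.6. Those intervals do not come near each other. This stands. A reader might infer that a tool missing one in five cases would pass as equivalent to one missing one in twenty. The protocol does not support that: it gives the De Long p-value no role as a decision rule and does not treat non-significance as equivalence. Selection is by experts, networks and PPI. The decision modelling in section 4.5 also addresses the relative value of the two errors.

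Two further limits stand. It would be too strong to say that De Long's test can never register a trade-off, since it rejects in 66% to 94% of studies for 95/70 against 80/80. It would also be too strong to say that no other comparison is planned. Section 5.1 leaves full analysis details to an SAP that is not available here, and that SAP may add paired tests.

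What the reply does not answer is that separate intervals are not a paired comparison on the same patients. That matters most for gaps smaller than those above. The protocol itself has also already fixed a method that targets the wrong quantity.

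**Conclusion.** The point holds as a mismatch between the named test and the stated outcomes. For tools coded positive or negative, De Long's test compares only (sensitivity + specificity)/2. It rejects at about the 5% level for fully offsetting differences of 10 to 18 points and in 16% to 24% of studies for a nearly offsetting one. Paired tests of each component reject in about 100% in the same settings. A significant De Long result does not identify the component that differs.

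This rests on binary coding as written in section 5.1, the planned 800 and 2,000 cases, and an assumed two-sided 5% level. The unknown agreement between tools does not alter the conclusion, since both extremes give the same picture. The primary estimates are sound, and the documents do not show that the choice of tool would go wrong. The change is worth making before analysis, but the study's validity does not depend on it.

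**What to change.** Replace the De Long sentence in section 5.1 with wording such as: *Tools will be compared by paired differences with 95% CIs (McNemar-type), separately for sensitivity among reference standard positives and for specificity among reference standard negatives; c-statistics will be descriptive.*

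Sampling weights are needed for specificity only if the sampling fraction of negatives differs between networks or strata. At the planned 500 of about 25,000 per network (2% in each) they change nothing.

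The cost is one sentence in the protocol, carried into the SAP. No new data or larger sample is needed. The downside is two comparisons per pair of tools instead of one, and so more multiplicity when many tools are compared.
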